Note: This document is signed electronically through submission and approval by the Principal Investigator in the University of Utah IRB Electronic Research Integrity and Compliance Administration (ERICa) system.

STUDY SUMMARY

Title	Image-Guided Salvage Oligometastasectomy and Radiation Therapy in Recurrent Prostate Cancer
Short Title	SOAR
Protocol Identifiers (IRB – internal)	IRB #115811 HCI-17-GU-26
IND number	Exempt
Phase	Phase II pilot
Design	This study is establishing baseline data for these patients who have no defined standard of care currently
Study Duration	5 Years total study duration: 2 years for accrual and 3 years for follow up
Study Center(s)	Single-center
Objectives	Primary objective 
• To assess response to treatment of oligometastatic disease. Secondary objectives: 
• To assess additional measurements of response to treatment of oligometastatic disease• To assess PSA progression free-survival following treatment of oligometastatic disease.• To assess time to disease recurrence.• To assess time to initiation of ADT for metastatic prostate cancer following treatment of oligometastatic disease.• To assess the rate of undetectable PSA following treatment of oligometastatic disease in subjects who have been previously undergone prostatectomy.• To assess safety.• To assess the impact of study treatment on change in quality of life over three years.
Number of Subjects	20
Diagnosis and Main Eligibility Criteria	Diagnosis Histologically proven adenocarcinoma of the prostate Inclusion Criteria 
• Recurrent adenocarcinoma of the prostate:
• Post-prostatectomy (with/without adjuvant radiotherapy): Patients must have a detectable or rising PSA level that is >0.05 ng/mL, with a second confirmatory level that is >0.05 ng/mL after a minimum of 1 week.
○ Post radiotherapy/ablation: PSA rise ≥ 2 ng/mL over nadir.• Subjects treated with prior definitive radiotherapy for prostate cancer who have positive molecular imaging (e.g., fluciclovine PET/CT or PSMA PET/CT scan or other per PI discretion)

	
suggesting recurrent intraprostatic disease must undergo TRUS biopsy less than or equal to one year before study enrollment:
 
 ○ If the TRUS biopsy is negative, no additional treatment is required to the prostate in addition to that of scan-positive sites. ○ If the TRUS biopsy is positive, subject must undergo salvage prostatectomy or salvage radiotherapy to the primary site concurrently with the study treatment per the treatment protocol algorithm. ○ Note: Biopsy is not required for prostate fossa recurrences after radical prostatectomy. 
 ● Oligometastatic disease defined as 10 or fewer metastatic lesions to lymph nodes and/or bones only. ● For patients with oligometastatic disease involving lymph node, metastasis is confined to the pelvic or para-aortic (below IMA) regions on¹- molecular imaging (e.g., fluciclovine PET/CT or PSMA PET/CT scan or other per PI discretion), CT, or MRI). ● Subjects must be candidates for surgery if indicated per the treatment algorithm. ● ECOG Performance Status ≤ 2 
Exclusion Criteria
 
 ● Known brain or visceral metastases other than lymph nodes ● Patients actively receiving hormone therapy for prostate cancer. Patients may have received hormone therapy previously but must have documented non-castrate levels of testosterone (>50 ng/dL) ● Prior or concurrent malignancy whose natural history or treatment, in the opinion of the enrolling investigator, may have the potential to interfere with the safety or efficacy assessment of the investigational treatment protocol of this study. ● Use of finasteride within 30 days prior to initiation of therapy. ● Use of dutasteride within 90 days prior to initiation of therapy. ● Active, uncontrolled, significant intercurrent or recent illness
Study Product, Dose, Route, Regimen	Oligometastasectomy and/or bone radiotherapy and/or nodal radiotherapy and/or prostatectomy
Duration of administration	Surgery: 1 day Radiotherapy: up to 8 weeks
Reference therapy	There is no reference therapy. This is a pilot study to determine a baseline response to the study population.
Statistical Methodology	The planned sample size is N = 20 evaluable subjects. The primary outcome variable of reduction in PSA $\geq 50\%$ at 6 months will be analyzed descriptively via 90% and 95% exact binomial confidence intervals. No hypothesis test will be performed on the primary outcome variables. The sample size is justified by the width of the 95%

	confidence intervals. We anticipate that the PSA 50% response rate at 6 months will be 30% based on the results published by Siriwardana, as their PSA response at 6 weeks and 12 months was 43% and 23% respectively. However, the definition used here is somewhat different than the definition in that clinical study. If the observed PSA 50% response rate is 30% (6/20), the 95% exact binomial confidence interval (Clopper-Pearson) will be 12% to 54 %. With 20 evaluable subjects the maximum width of a 95% exact binomial confidence interval is 46% (27% to 73%) and occurs when the observed response rate is 50% (10/20).
--	---

SCHEMA

Figure 1: Overall Treatment Schema (All Arms)

[figure not shown]
[figure not shown]

Figure 2: Adjuvant radiotherapy (Arms B and C only)

1. With completion of prostate radiotherapy (for patients who received an incomplete definitive radiation course) OR salvage prostatectomy if positive baseline TRUS biopsy (including subjects enrolled in Arm A)
2. Bone radiotherapy can be completed prior to surgical resection if indicated in the opinion of the investigator.
3. Ipsilateral involved-field radiotherapy to 45 Gy in 25 fractions using image-guided IMRT
4. Simultaneous integrated boost to gross target volumes to be ≥ 76 Gy EQD2
5. Target volume defined with inferior dosimetric border set immediately above the previously treated area. Nodal volumes will be treated to 50.4 Gy. The prostate fossa will be treated for post-prostatectomy patients who have not had any radiation to the prostate fossa.

1 OBJECTIVES

1.1 Primary Objective

To assess response to treatment of oligometastatic disease.

Primary Endpoints: proportion of subjects with a reduction in PSA $\geq 50\%$ 6 months after completion of all treatment (salvage and adjuvant therapy).

1.2 Secondary Objectives

1.2.1 To assess additional measurements of response to treatment of oligometastatic disease.

Secondary Endpoints: Proportion of subjects with reductions in PSA $\geq 50\%$ 12 months after and $\geq 90\%$ 6 and 12 months after completion of all treatment (salvage and adjuvant therapy).

1.2.2 To assess PSA progression free-survival following treatment of oligometastatic disease.

Secondary Endpoint: Proportion of subjects without PSA progression (defined using Prostate Cancer Working Group 3 Criteria PCWG3), evaluated every 3 months for 3 years after completion of all treatment (salvage and adjuvant therapy).

1.2.3 To assess time to disease recurrence following treatment of oligometastatic disease.

Secondary Endpoint: The time from study enrollment until the date of confirmed radiographic disease progression as defined by RECIST 1.1 and PCWG3.

1.2.4 To assess time to initiation of ADT for metastatic prostate cancer following treatment of oligometastatic disease.

Secondary Endpoint: The time from study enrollment to the initiation of ADT.

1.2.5 To assess the rate of undetectable PSA following treatment of oligometastatic disease in subjects who have previously undergone prostatectomy.

Secondary Endpoint: In subjects who have previously undergone prostatectomy evaluate the proportion of patients with a PSA ≤ 0.2 ng/mL, evaluated 6 and 12 months after completion of all treatment (salvage and adjuvant therapy).

1.2.6 To assess safety.

Secondary Endpoint: Rate of AEs and SAEs as defined by CTCAE version 5.0.

1.2.7 To assess the impact of study treatment on change in quality of life over three years.

Secondary Endpoint: Quality of life (QOL) questionnaires (FACT-P and Expanded Prostate Cancer Index Composite EPIC-26) will be administered at screening, the Response Assessment Visit, and each follow-up visit.

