5.1 Inclusion Criteria

Yes/No (Response of "no" = subject ineligible)

5.1.1 _____ Male subjects age \geq 18 years.

5.1.2 _____ Histologically proven adenocarcinoma of the prostate.

5.1.3 _____ Recurrent prostate carcinoma after definitive therapy for primary disease defined as:

- Post-prostatectomy (with/without adjuvant radiotherapy): Patients must have a detectable or rising PSA level that is >0.05 ng/mL, with a second confirmatory level that is >0.05 ng/mL after a minimum of 1 week.
- Post radiotherapy/ablation (without radical prostatectomy): PSA rise ≥ 2 ng/mL over nadir.

5.1.4 _____ Subjects treated with prior definitive radiotherapy for prostate cancer who have positive molecular imaging (e.g., fluciclovine PET/CT or PSMA PET/CT scan or other per PI discretion) suggesting recurrent intraprostatic disease must undergo TRUS biopsy less than or equal to one year before study enrollment:

- If the TRUS biopsy is negative, no additional treatment is required to the prostate in addition to that of scan-positive sites.
- If the TRUS biopsy is positive, subject must undergo salvage prostatectomy or salvage radiotherapy to the primary site concurrently with the study treatment per the treatment protocol algorithm.
- Note: Biopsy is not required for prostate fossa recurrences after radical prostatectomy.

5.1.5 Oligometastatic disease defined as 10 or fewer metastatic lesions to lymph nodes and/or bones only.

5.1.6 For patients with oligometastatic disease involving lymph nodes, metastasis is confined to the pelvic or para-aortic (below IMA) regions on molecular imaging (e.g., fluciclovine PET/CT or PSMA PET/CT scan or other per PI discretion).

5.1.7 All subjects must be surgical candidates if surgery is indicated per the treatment algorithm.

5.1.8 ECOG Performance Status ≤ 2 .

5.1.9 Use of condoms for male subjects who have not had surgical removal of their prostate and have a partner of child bearing potential beginning at the time of ICF signature and lasting until at least 6 months after the last radiation treatment. Because of the potential side effect on spermatogenesis associated with radiation, female partners of childbearing potential must agree to use a highly effective contraceptive method during and for 6 months after completing treatment.

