6.2.1 Oligometastasectomy

Subjects with pelvic or para-aortic lymph node metastases will undergo surgical dissection. Treatment will cover the bilateral nodal group identified by molecular imaging (e.g., fluciclovine PET/CT or PSMA PET/CT scan or other per PI discretion), and one level above and one level below any identified nodal region.

Nodal groups from distal to proximal include: 1) Obturator fossa, 2) External iliac, 3) Common iliac, 4) Aortic-below IMA, 5) Aortic-above IMA.

Metastases to superficial inguinal nodes will also be considered for surgical dissection in which cases both a superficial inguinal lymph node dissection and pelvic lymph node (obturator fossa and external iliac nodes) dissection will be performed.

For subjects who were treated with definitive radiotherapy pre-study and have a positive TRUS biopsy at baseline, or less than or equal to a year before study enrollment, salvage prostatectomy will be performed along with the procedure described above (unless salvage radiotherapy is indicated as described in Section 3.2.1).

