6.2.3.1 Subjects whose PSA declines to 0 following resection

This will be considered a complete PSA response (PSA CR) and no further treatment will be required. Subjects will move on to the follow-up phase of the study as described in Section 9.3.

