6.2.3.3 Subjects whose PSA declines by < 1/3

This will be considered a treatment failure (PSA response failure), no adjuvant therapy will be given. Subjects will enter the follow-up period until diagnosis of metastatic disease and will not receive any further treatment.

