10.3.2 Rate of Undetectable PSA

The rate of undetectable PSA is defined as the proportion of patients ever treated with prostatectomy whose PSA remains ≤ 0.2 ng/mL after 6 and 12 months following completion of treatment (salvage \pm adjuvant).

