11.3 Statistical Hypotheses and Analyses

This study is establishing baseline data for patients who have no defined standard of care therapy. All study data will use descriptive statistics and will be exploratory only.

Since this study is not using any hormonal therapy, we expect that using PSA analysis will be accurate and provide an early readout regarding the potential efficacy and clinical utility of this approach.

Primary Objective

The primary endpoint is the proportion of subjects with a reduction in PSA $\geq 50\%$ 6 months after completion of all treatment (salvage and adjuvant therapy). The observed proportion and a 95% exact binomial confidence interval will be reported for the entire group of evaluable patients (Arms A, B and C together) as well as for each cohort separately.

Secondary Objectives

1. 95% exact confidence intervals will be reported for the observed proportions with reductions in PSA $\geq 50\%$ 12 months after and $\geq 90\%$ 6 and 12 months after completion of all treatment (salvage and adjuvant therapy). This will be done for the entire group of evaluable patients (Arms A, B and C together) as well as for each Arm separately.
2. The proportion of subjects without PSA progression (defined using Prostate Cancer Working Group 3 Criteria PCWG3), will be evaluated every 3 months for 3 years after completion of all treatment (salvage and adjuvant therapy) and analyzed using Kaplan-

Meier methodology. This will be done for the entire group of evaluable patients (Arms A, B and C together) as well as for each Arm separately.

3. The time from study enrollment until the date of confirmed radiographic disease progression as defined by RECIST 1.1 and PCWG3 will be analyzed using Kaplan-Meier methods. This will be done for the entire group of evaluable patients (Arms A, B and C together) as well as for each Arm separately.
4. The time from study enrollment to the initiation of ADT will be analyzed using Kaplan-Meier methods. This will be done for the entire group of evaluable patients (Arms A, B and C together) as well as for each Arm separately.
5. The proportion of patients with a PSA ≤ 0.2 ng/mL will be evaluated 6 and 12 months after completion of all treatment (salvage and adjuvant therapy) in the subset of patients who have previously undergone prostatectomy. This will be done for the entire group of evaluable patients (Arms A, B and C together) as well as for each Arm separately.

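### The undetectable-PSA endpoint (≤ 0.2 ng/mL) has no baseline condition or split, although post-prostatectomy subjects may enter already meeting it

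*Combined protocol and SAP*

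**What the plan says.** **Endpoint.** Section 1.2.5 is to "evaluate the proportion of patients with a PSA ≤ 0.2 ng/mL, evaluated 6 and 12 months after completion of all treatment", among subjects with a previous prostatectomy. Section 10.3.2 describes the "proportion of patients ever treated with prostatectomy whose PSA remains ≤ 0.2 ng/mL" at the same two visits. Section 11.3, item 5, analyses the proportion "in the subset of patients who have previously undergone prostatectomy", overall and by arm. None of the three refers to baseline PSA. The response-evaluable population in 11.2.2 is defined by completion of treatment, with no PSA condition.

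**Entry.** For post-prostatectomy recurrence, section 5.1.3 states: "Patients must have a detectable or rising PSA level that is >0.05 ng/mL", with a second value above the same level at least one week later. No higher minimum is set. The other route is "Post radiotherapy/ablation (without radical prostatectomy): PSA rise ≥ 2 ng/mL over nadir".

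**Response labels in the nodal arms.** Section 6.2.3.1 ("Subjects whose PSA declines to 0 following resection") makes a fall to zero a complete PSA response. Section 6.2.3.3 says of a fall of less than one third: "This will be considered a treatment failure (PSA response failure), no adjuvant therapy will be given".

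**The concern.** The entry range and the success range overlap. A subject who enters between the two limits is a success at 6 or 12 months if nothing happens to his PSA, and can be one if it rises. The label adds to the difficulty: eligibility treats a value just above 0.05 ng/mL as evidence of detectable or rising PSA, while the endpoint calls anything up to 0.2 undetectable.

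The objective concerns the rate after treatment, and section 2 says the trial should provide a reference for later studies. There is no control arm in which a baseline artefact would cancel. A later trial with a different share of low entrants could not interpret the pooled rate.

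A smaller point concerns the denominator. Sections 1.2.5 and 11.3 refer to prostatectomy undergone previously; 10.3.2 refers to prostatectomy at any time. An operation before enrollment satisfies both. One done on study (6.2.1: "salvage prostatectomy will be performed along with the procedure described above") is left open.

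**Working it through.** **The plan's own figures.** No figure is stated for this endpoint. The exact (Clopper-Pearson) 95% intervals in section 11.1 reproduce: 6/20 gives 11.9% to 54.3% (stated 12% to 54%), and 10/20 gives 27.2% to 72.8%, width 45.6 points (stated 46), the maximum at n = 20.

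**Overlap.** Entry requires PSA > 0.05 (5.1.3); success requires PSA ≤ 0.2 (1.2.5). The overlap is 0.05 < PSA ≤ 0.2 ng/mL. Entrants by the post-radiotherapy route are at least 2 ng/mL above nadir, so they cannot be in it.

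**One subject across the endpoints.** Take a nodal-arm subject who enters at 0.10 and stands at 0.19 six months after treatment.

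| Rule | Result |
|---|---|
| 1.2.5, PSA ≤ 0.2 | success |
| PSA50 and PSA90 (1.1, 1.2.1) | non-responder: no fall |
| PSA progression (10.2.1) | not flagged: needs a rise of at least 2 ng/mL |
| 6.2.3.3, if the fall after salvage therapy was under one third | PSA response failure |

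**Effect of one low entrant.** Let n be the number of prostatectomy subjects, including one low entrant, and x the successes among the n − 1 who entered above 0.2. If the low entrant stays at or below 0.2, the reported rate is (x + 1)/n, against x/(n − 1) among those who could convert:

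gain = (x + 1)/n − x/(n − 1) = (n − 1 − x) / (n(n − 1)), which is at most 1/n (at x = 0).

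| n | x | Gain (percentage points) |
|---|---|---|
| 20 | 0 | 19/380 = 5.0 |
| 20 | 4 | 15/380 = 3.9 |
| 20 | 10 | 9/380 = 2.4 |
| 12 | 0 | 11/132 = 8.3 |
| 12 | 4 | 7/132 = 5.3 |
| 7 | 0 | 6/42 = 14.3 |
| 7 | 4 | 2/42 = 4.8 |

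All three n are assumptions. n = 20 supposes that every evaluable subject had a prior prostatectomy; 12 stands for a subset and 7 for a single arm, since item 5 is also reported by arm.

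The effect can go the other way. If the low entrant rises above 0.2, then at n = 20, x = 4 the rate is 4/20 = 20.0% against 4/19 = 21.1%, a loss of 1.1 points.

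**Several low entrants.** Assume n = 20, x = 4 and k low entrants who all stay low:

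| k | Reported, (4 + k)/20 | Among those entering > 0.2, 4/(20 − k) |
|---|---|---|
| 1 | 25.0% | 4/19 = 21.1% |
| 2 | 30.0% | 4/18 = 22.2% |
| 4 | 40.0% | 4/16 = 25.0% |

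**Extreme case.** Assume 15 prostatectomy subjects, 3 entering at or below 0.2 and unchanged, none of the other 12 converting. The endpoint as written gives 3/15 = 20% (95% exact interval 4% to 48%). Among those entering above 0.2 it is 0/12 (0% to 26%).

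**The case against.** The strongest reply is that the endpoint is a landmark status and not a conversion rate. Section 10.3.2 speaks of PSA that remains at or below 0.2, and on that reading a subject with recurrent disease who is still there at 6 or 12 months belongs in the numerator. The rate is computable as written, and choosing conversion as the target is a choice of estimand. This is fair as far as it goes, and it is the reason to keep the all-subject rate. It does not make that rate enough on its own: the objective concerns what follows treatment, and the pooled figure cannot show how many subjects got there after it.

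Several further points stand as limits on size:

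- The gains above treat every low entrant who stays low as an artefact. One who falls from 0.15 to 0 is a true responder, so the figures are upper bounds per low entrant.
- Treatment is assigned on visible nodal or bone lesions, which may leave few low entrants or none.
- Every analysis is descriptive. PSA50 and PSA90, reported at the same visits, require a real fall. Section 4.1 limits the aim to a preliminary reference for response rate and duration, and 10.1 defines the response rate by a 50% decline.
- The failure label in 6.2.3.3 guides adjuvant therapy soon after salvage treatment. It is a different rule at a different time, so the contrast illustrates the problem but is not a formal contradiction.

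None of this removes the overlap.

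**Conclusion.** The concern holds. Followed exactly, the definition can score an unchanged or rising PSA as a success, and no section separates such subjects from those who reached 0.2 or below after treatment. The overlap is certain from the text; its numerical effect is not. That depends on the number of post-prostatectomy subjects, how many enter between 0.05 and 0.2 ng/mL, and how many of those stay there, none of which the documents give. The effect is zero with no low entrants and otherwise at most 1/n for each one who stays low. The consequence is confined to this secondary endpoint; the primary analysis and the sample size are untouched. It should be fixed because the correction is cheap and the rate is the only result this objective will deliver.

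**What to change.** - Keep the 0.2 ng/mL cut-off and the all-subject rate.
- Pre-specify reporting by screening PSA, > 0.2 versus ≤ 0.2 ng/mL. Take the upper stratum as the rate of reaching 0.2 or below after treatment.
- In the lower stratum give the number of subjects, how many remain at or below 0.2, and each subject's change from baseline, so that a true fall such as 0.15 to 0 stays visible.
- Call the endpoint PSA ≤ 0.2 ng/mL instead of undetectable PSA.
- Use one denominator wording in 1.2.5, 10.3.2 and 11.3, and say whether salvage prostatectomy done on study counts. Those subjects enter by the post-radiotherapy route, so they would fall in the upper stratum.

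**Cost.** Wording in three sections and no new data: the study calendars already require screening laboratory tests, including PSA, within 2 weeks before enrollment. The drawbacks are small strata and possibly a less favourable rate of reaching 0.2 or below. Item 5 specifies no interval; if 95% exact intervals are added, the widest is 46 points at n = 20, 51 at n = 16, 58 at n = 12 and 65 at n = 9. The all-subject rate keeps its full denominator.

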1.3 Exploratory Objective(s)

To assess the correlation of molecular biomarkers with clinical response and resistance to surgery and radiation therapy.

Exploratory Endpoint(s): Evaluation for genomic alterations or abnormal protein expression that correlates with radiation resistance or predilection for early metastasis and worse overall prognosis.

2 BACKGROUND

Most subjects diagnosed with localized prostate cancer are cured with definitive surgery or radiation therapy. However, a significant proportion experience disease progression despite these interventions. Typically subjects will initially have a PSA only relapse, without radiographic evidence of metastatic disease. There is no definitive standard of care for these subjects proven to improve clinical outcomes. Some subjects are treated with immediate androgen deprivation therapy (ADT) either through intermittent or continuous administration. Other subjects are carefully observed until radiographic metastatic disease progression. It is not clear which treatment strategy, if any, is clinically superior. Some studies suggest that immediate therapy may lead to superior clinical outcomes. Duchesne and colleagues¹ reported results from a phase III randomized clinical trial enrolling 293 men total, including de-novo incurable disease and those with a PSA relapse. Subjects were treated with either immediate or delayed ADT. In the PSA relapse population, 137 subjects were treated with delayed ADT while 124 were treated with immediate ADT. The estimated five year survival was 78.2% (95% CI, 67.2% – 85.8%) compared to 84.3% (95% CI, 73.9% – 90.8%) (P = 0.10) for the delayed versus immediate treatment groups respectively, suggesting a possible benefit based on this small study. In contrast, other studies do not support a clinical benefit from immediate therapy. Garcia-Albeniz et al² reported on 2096 subject outcomes with immediate compared to deferred ADT. There was no improvement to the 5-year prostate cancer specific survival, 92.8% (95% CI, 86.7% – 98.9%) and 95.8% (95% CI, 92.7% – 98.9%) respectively for immediate and delayed ADT. There is a distinct lack of clear, clinical evidence to guide treatment decisions in this population.

Further complicating the clinical decision making, recently advanced, molecular imaging techniques have been FDA approved or are in the approval process for subjects with PSA only relapse. The ¹⁸F-fluciclovine PET scan (also called axumin or [¹⁸F] anti-FACBC PET scan) is one example. It is approved specifically in subjects with PSA only relapsed prostate cancer. Unfortunately, there is very limited clinical data to guide any treatment recommendations for these subjects with ¹⁸F-fluciclovine PET positive disease. Different approaches appear to be used, such as continued observation, focal radiation therapy, surgical resection or immediate hormonal therapy. There are two reports of institutional experience using radiation or surgery approaches for subjects with a PSA only relapse and oligometastatic disease identified on molecular imaging.

Bouman-Wammes et al³ reported on stereotactic body radiation therapy (SBRT) in forty-three subjects with oligometastatic (defined as < 5 metastasis) hormone sensitive prostate cancer. This was a single arm, prospective study. Subjects were identified through ¹⁸F-fluoromethylcholine positron emission tomography (PET) scans. A PSA response was seen in 67.4% of subjects, and the median ADT-free duration was 15.6 months (95% CI, 11.7 – 19.5 months), but 25.7 months (95% CI, 9.0 – 42.4 months) for subjects with a PSA response. Clinical outcomes were

compared against historic controls. The time until castration resistant prostate cancer was longer for the SBRT-treated subjects with a mean of 66.6 months (95% CI, 53.5 – 79.8 months), compared to 36.41 months (95% CI, 26.0 – 46.8 months) for the historic controls (P = 0.020). There were no significant toxicities associated with this treatment in this study.

Siriwardana⁴ and colleagues enrolled 35 subjects with oligometastatic disease identified by ⁶⁸Ga-PSMA PET scans. Subjects underwent a targeted pelvic dissection (PET positive lesions only), unilateral extended dissection or a bilateral extended dissection. 32 subjects (91%) had pathologically confirmed lymph node metastasis. Subjects with a bilateral extended dissection appeared to benefit from this intervention on univariate analysis, suggesting that many subjects with biochemical recurrence have limited regional disease metastasis and may benefit from aggressive local therapy.

Recently two clinical trials have demonstrated substantial clinical benefit for early, intense treatment for subjects with metastatic hormone sensitive prostate cancer using a combination of ADT plus abiraterone (NCT00268476, NCT01715285). Intensive treatment with combination ADT and chemotherapy (NCT00309985) has similarly been demonstrated to improve clinical outcomes in subjects with metastatic hormone sensitive prostate cancer. Additionally, early treatment in patients with non-metastatic castration-resistant prostate cancer with either enzalutamide⁵ or apalutamide⁶ compared with placebo both demonstrated a significant improvement to metastasis-free survival and a similar trend for improved overall survival. This body of evidence strongly suggests that early, intense therapy may provide significant clinical benefit in subjects with hormone sensitive oligometastatic prostate cancer.

We hypothesize that local salvage treatment of oligometastatic disease identified on advanced imaging will result in long-term disease control, including optimal PSA responses and prolongation of radiographic progression-free survival. These results might translate into some men obtaining a cure of their prostate cancer, though this will have to be validated in future studies and with longer clinical follow up. Given that there is no standard of care for this setting, this clinical trial is designed to establish a standard reference for this population that can be used as the basis for additional clinical investigations in the future.

